11.4 Deaths and Serious Adverse Events

A by-listing will be generated to provide subject-specific details on subjects who died.

The following summaries will be provided for Treatment Period 2 and the RWS Analysis Set. In addition, a summary for C1-INH over the whole study for RWS Analysis Set and a summary across the whole study will be given for the RiS Analysis Set:

- Serious TEAEs,

- Serious TEAEs related to Study Treatment.

The following listings will be provided for RiS Analysis Set:

- Serious Non-TEAEs,
- Serious TEAEs,
- TEAEs resulting in death.

11.5 Adverse Events Leading to Discontinuation of Study Treatment, Withdrawal from the Study, and Other Significant Adverse Events

The following listings will be provided based on RiS Analysis Set:

- TEAEs Leading to Discontinuation of Study Treatment,
- Non-TEAEs leading to Withdrawal from the Study,
- TEAEs leading to Withdrawal from the Study.

11.6 Pregnancies

While pregnancy itself is not considered to be an AE or SAE, any pregnancy complication or elective termination of a pregnancy for medical reasons will be recorded as an AE or SAE as described in the protocol. If any subject OR any subject or subject's partner becomes pregnant while on the study, the information will be included in the narratives and no separate table or listing will be produced.

11.7 Clinical Laboratory Evaluations

11.7.1 Clinical chemistry

All clinical chemistry parameters for this study will be summarized by scheduled visit using descriptive statistics. All unscheduled visits will be excluded from these by-visit summaries.

Open-label clinical chemistry data for Period 1 and that for the entire study will be summarized for the RiS Analysis Set. Double-blind clinical chemistry data for Period 2 will be summarized for the RWS Analysis Set by treatment.

The estimated and CCI [REDACTED] eGFR will be summarized as part of efficacy, and not part of safety.

Clinical Chemistry parameter to be summarized: Albumin, alkaline phosphatase, ALT, AST, total bilirubin, BUN, calcium, carbon dioxide, chloride, creatinine, glucose, potassium, sodium, and protein (total).

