10.3.4.2 Other safety evaluations

Clinical laboratory parameters for this study will be summarized by scheduled visit using descriptive statistics or frequency counts and percentages, as appropriate. Vital signs will be summarized similarly.

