6.7 CCI

CCI

7 General Considerations

Analysis datasets will be created according to CDISC standards, and data will be displayed according to reporting standards in this SAP and tables, figures and listings (TFL) formats.

SAS version 9.3 or higher will be used to perform all data analyses and to generate TFLs.

All ICH required data in the database will be presented in data listings.

Continuous variables will be summarized in terms of the number of observations, mean, standard deviation, median, Q1, Q3, minimum and maximum. Other descriptive statistics (eg, quartiles, coefficient of variation) may be reported when appropriate. Categorical variables will be summarized using frequency counts and percentages. Analyses that use other descriptive statistics will have the specific descriptive statistics required identified with the analysis in the applicable SAP section.

All listings will include subject number, treatment group. The laboratory normal reference ranges will be provided and clinical laboratory test results outside the normal reference range will be flagged in the laboratory data listings.

Summary statistics of central tendency will be reported to one more decimal place than the collected data. Summary statistics of variability will be reported to one more decimal place than the commensurate measure of central tendency. For example, the mean and median for age will be reported to one decimal place because it is collected in full years. The standard deviation of age will then be reported to 2 decimal places.

Formatting for dates and times will be: descriptive percentages and proportions will be displayed to one decimal place. Percentages and proportions to be tested will be calculated to 4 decimal places. Durations for events will be display to 1 decimal place.

- Dates only – ddmmmyyyy
- Times only – hh:mm or hh:mm.ss
- Dates and times – ddmmmyyyy hh:mm or ddmmmyyyy hh:mm:ss

In general, only scheduled visits will be included in by-visit summaries. However, worst-case or best-case values (as appropriate) will be derived using both scheduled and unscheduled visits. In general, assessment windows will not be defined for the purpose of classifying measurements obtained outside scheduled assessment times, other than those indicated in the Schedule of Assessments. However, exceptions may apply for creatinine / eGFR.

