8.2.5 Baseline Definition

Baseline for non-laboratory and laboratory data (except creatinine for eGFR) is defined as the most recent, non-missing value prior to or on the first study treatment dose date/time in Treatment Period 1 (for non-laboratory it is referred to eCRF data and for laboratory data it is referred to local laboratory data).

For subjects who did not receive study treatment during the study, a baseline value will not be calculated. The most recent, non-missing value prior to or on the study treatment dose date / time is based on scheduled assessments only.

Baseline eGFR has been defined as follows in original protocol and amendments:

- For subjects randomized prior to Protocol Amendment 1, dated November 28, 2017, the nadir (minimum) of the eGFR values from screening and Day 1 will be used as the baseline.
- For subjects randomized after Protocol Amendment 1 the mean of the screening and Day 1 values will be used as the baseline.

For the purpose of analysis, baseline eGFR is defined as the mean of the screening and Day 1 values.

Note that a set of vital signs or laboratory values may have different dates for baseline values.

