11.7.2 Hematology

All hematology parameters for this study will be summarized by scheduled visit using descriptive statistics. All unscheduled visits will be excluded from these by-visit summaries.

Open-label hematology data and that for the entire study will be summarized for the RiS Analysis Set.

Double-blind hematology data will be summarized for the RWS Analysis Set by treatment.

Hematology parameter to be summarized: Hemoglobin, hematocrit, red blood cell indices: mean corpuscular hemoglobin, mean corpuscular hemoglobin concentration, mean corpuscular volume, blood cell counts: basophils, eosinophils, erythrocytes, leukocytes, lymphocytes, monocytes, neutrophils, neutrophil band forms, platelets, and reticulocytes.

DSA: will be included as efficacy endpoint and will therefore be summarized for efficacy.

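### SAP 11.7 gives no laboratory summary relative to the reference range or to the pre-randomization value; out-of-range status and unscheduled results appear only in listings

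*SAP*

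**What the plan says.** - **Table rule.** Under SAP 11.7.1, chemistry is "summarized by scheduled visit using descriptive statistics. All unscheduled visits will be excluded from these by-visit summaries". SAP 11.7.2 says "All hematology parameters for this study will be summarized by scheduled visit using descriptive statistics" and also leaves out unscheduled visits. Neither section asks for anything else.
- **Protocol rule.** Protocol 10.3.4.2 says: "Clinical laboratory parameters for this study will be summarized by scheduled visit using descriptive statistics or frequency counts and percentages, as appropriate".
- **Source of the values.** SAP 8.2.5 defines the laboratory baseline and states that "for laboratory data it is referred to local laboratory data". Protocol Table 1 (footnote h) and Table 13 place the biochemistry panel in the local laboratory. SAP 7.1 pools all sites.
- **By-arm tables.** "Double-blind clinical chemistry data for Period 2 will be summarized for the RWS Analysis Set by treatment" (SAP 11.7.1), and "Double-blind hematology data will be summarized for the RWS Analysis Set by treatment" (SAP 11.7.2). Open-label and entire-study laboratory tables use the Run-in Safety (RiS) set, without arms.
- **General conventions.** SAP 7 says that "worst-case or best-case values (as appropriate) will be derived using both scheduled and unscheduled visits". It assigns reference ranges and out-of-range flags to the listings. SAP 8.2.6 defines change from baseline, but 11.7 does not call for it.

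**The concern.** Safety of C1-INH is a secondary objective, and formal testing was dropped after termination, so the descriptive tables carry the whole safety comparison. A laboratory table should let a reader see how many subjects went outside the normal range, how far, and whether they were already there before randomized treatment. The tables in 11.7 answer none of these. They show raw values from several local laboratories on one scale, and they omit any sample taken between scheduled visits. The TP2 comparison by arm also starts after randomization, so a difference already present at Week 12 cannot be told apart from one that arose in TP2. The general convention on worst-case values in SAP 7 would fill part of the gap, but no laboratory output uses it.

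**Working it through.** The plan states no figure on this point, so there is none to reproduce. The check compares sections and then tests whether the cost of excluding unscheduled values can be sized.

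**1. Summaries relative to the reference range.** Ranges and flags enter only through the listings (SAP 7). Section 11.7 reports the standard set of statistics, including quartiles and extremes. A minimum or maximum is a raw value and does not show whether the result was outside the range of the laboratory that reported it. It also does not count subjects: the maxima at three visits may belong to one subject or to three. That panel values are local is stated for the baseline and for the panel itself; that 11.7 uses them without normalization is an inference, because 11.7 names neither a source nor a normalization.

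**2. Summaries relative to the pre-randomization value.** The last scheduled chemistry and hematology before randomization are at Week 12 (Protocol 8.5.3.13). At Week 13, blood is drawn only for early withdrawals (8.5.3.14). SAP 11 classes findings dated before randomization as open-label, so Week 12 falls in the RiS tables, which mix later responders and non-responders and have no arms. The opening of SAP 11 adds a whole-study safety summary for randomized subjects on C1-INH; placebo has no counterpart. For vital signs, SAP 11.8.1 does give entire-study results by treatment.

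**3. Can the effect of excluding unscheduled values be sized?** Suppose an abnormality lasts D, with onset uniform over the period. The durations are assumptions.

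- TP2 runs from Week 13 to Week 38, 25 weeks, with panels at Weeks 20, 28 and 38 (Protocol 8.5.4). For D up to 7 weeks, the share meeting a scheduled draw is 3D/25. For D = 2 weeks: 6/25 = 24%. For D = 4 weeks: 12/25 = 48%.
- TP1 hematology is drawn on Days 1, 7 and 14 and at Week 12 (Day 84), over 83 days. For D of 2 or 4 weeks, onsets over the 13 days from Day 1 to Day 14 are caught, plus those in the D days before Day 84. The share is (13 + D)/83. For D = 14 days: 27/83 = 33%. For D = 28 days: 41/83 = 49%.
- TP1 chemistry is drawn on Days 1, 7 and 14 and then weekly to Week 12. No gap exceeds 7 days, so anything lasting a week or more is caught: 100%.

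These shares describe the draw schedule. The exclusion rule removes an episode from the tables only if an unscheduled sample was taken during it. If u is the chance of such a sample in an episode that missed the scheduled draws, the share removed in TP2 is (1 − 0.24)u = 0.76u for 2-week episodes and (1 − 0.48)u = 0.52u for 4-week episodes. The documents give no value for u. Over its full range from 0 to 1, the result runs from 0 to 76% and from 0 to 52%, so the effect cannot be quantified.

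**4. Scale.** SAP 3 reports 13 subjects randomized. If the arms hold 6 and 7 (an assumption), one subject is 1/6 = 17% or 1/7 = 14% of an arm.

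**The case against.** The strongest reply is that the information is nearly all there. TP2 laboratory data are tabulated by treatment with extremes. When a visit's sample is repeated to follow up an abnormal result, SAP 8.2.7 keeps the initial abnormal value. Listings hold every scheduled and unscheduled result with flags. Abnormalities that the investigator judges clinically significant must be recorded as adverse events (Protocol 9.1.1) and so reach the treatment-emergent tables in SAP 11.2. With 13 randomized subjects, a reader can go through the listings. All of this stands and limits the consequence. Two qualifications remain. The adverse event route depends on investigator judgement, and Protocol 9.1.1 exempts elevated creatinine and worsening renal function with its related laboratory changes.

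A reader might draw three stronger conclusions, which the documents do not support:

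- **That a between-arm difference in TP2 is shown nowhere.** The by-treatment tables in 11.7.1 and 11.7.2 show it; what they lack is a reference point.
- **That the SAP drops an analysis the protocol required.** The protocol offers frequency counts as an alternative, as appropriate, and descriptive statistics satisfy that wording.
- **That most short-lived abnormalities are lost because unscheduled values are excluded.** The low coverage in TP2 and in TP1 hematology comes mainly from the sparse schedule, does not apply to TP1 chemistry for episodes of a week or more, and cannot be recovered by any table where no sample was taken.

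**Conclusion.** The point holds as a gap in presentation. For chemistry and hematology, the plan specifies no summary relative to the reference range, no worst-value summary, and no by-arm TP2 summary relative to Week 12. Unscheduled values and range status are left to listings. The effect of the exclusion rule is unquantified, since the documents give no rate of unscheduled sampling. The conclusion rests on two readings: that 11.7 uses the local panel values as reported, and that the SAP's sections list all planned laboratory tables. No document shows how far assays or ranges differ between sites, so the distortion from pooling raw values is also unsized. With 13 randomized subjects and full flagged listings, this is a worthwhile improvement to a secondary safety objective and does not threaten the trial's conclusions.

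**What to change.** Keep the by-visit tables and add one shift table each to 11.7.1 and 11.7.2:

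- Count and percentage of subjects by worst post-baseline value, using scheduled and unscheduled samples under the SAP 7 convention, classed low, normal or high on the reporting laboratory's own range. Where both directions matter, show the lowest and highest values separately.
- For TP1, on the RiS set, as a shift from the 8.2.5 baseline.
- For TP2, on the Randomized Withdrawal Safety set and by arm, as a shift from the last value before the first TP2 dose (normally Week 12).

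The tables should include creatinine, because renal changes are exempt from adverse event recording.

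The cost is a few lines of SAP wording and two table shells. The values are already collected and the ranges are already planned for the listings. The downside is a few more output pages with small counts per cell, so counts should be read ahead of percentages.

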11.7.2 Hematology

All hematology parameters for this study will be summarized by scheduled visit using descriptive statistics. All unscheduled visits will be excluded from these by-visit summaries.

Open-label hematology data and that for the entire study will be summarized for the RiS Analysis Set.

Double-blind hematology data will be summarized for the RWS Analysis Set by treatment.

Hematology parameter to be summarized: Hemoglobin, hematocrit, red blood cell indices: mean corpuscular hemoglobin, mean corpuscular hemoglobin concentration, mean corpuscular volume, blood cell counts: basophils, eosinophils, erythrocytes, leukocytes, lymphocytes, monocytes, neutrophils, neutrophil band forms, platelets, and reticulocytes.

DSA: will be included as efficacy endpoint and will therefore be summarized for efficacy.

11.8 Other Safety Measures

11.8.1 Vital Signs

Systolic blood pressure, diastolic blood pressure, heart rate, and weight will be summarized for each scheduled visit using descriptive statistics or frequency counts as appropriate.

Vital signs during Treatment Period 1 will be summarized for the RiS Analysis Set. Vital signs for the entire study will be summarized for the RWS Analysis Set by treatment.

12 Pharmacokinetics

All non-compartmental analyses for the derivation of PK parameters will be performed according to [CSL SOP PK-GDL-01](#) and will be performed by CSL Behring Clinical Pharmacology & Pharmacometrics or their designate by using WinNonlin® version 8.1 or later.

All analyses in this section will be based on the PK population, unless otherwise stated.

The merge of PK concentration data and CRF data to generate a dataset with actual blood sampling times, nominal sampling times, actual time relative to dosing, and PK concentrations of

C1-INH antigen concentrations and C1-INH functional activity will be performed after data base lock by **PPD** and is specified in [Section 12.5](#).

12.1 PK Sampling Schedule

Blood samples will be taken for measurement of C1-INH antigen concentrations and C1-INH functional activity at the following time points of Day 10 of Treatment Period 1: pre-dose, 0 minutes (start of C1-INH infusion), 15 minutes, 3, 8, 24, and 72 hours after start of infusion and at Week 11 visit (Treatment Period 1) at time points of: pre-dose, 0 minutes (time of C1-INH injection), 24, 48, and 72 hours after injection. PK samples will be drawn in a subset of subjects.

Summary statistics will be provided by nominal (planned) time points.

Concentration data excluded from the derivation of PK parameters will be omitted from summaries and will be flagged with an asterisk in the relevant data listings, with a footnote to indicate that these values have been omitted from subsequent analyses.

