- ^f A pregnancy test will be conducted for women of childbearing potential, only. Serum pregnancy test will be conducted at Screening and Week 12. Urine or serum pregnancy tests will be conducted at all other timepoints. If the screening pregnancy test is conducted within 24 hours of Day 1, then an additional pregnancy test is not needed on Day 1.
- ^g A blood sample will be retained for potential future serology assessments.
- ^h Creatinine will be measured by the central laboratory ([CL]) and as a part of the serum biochemistry panel by the local laboratory. The complete list of assessments included as a part of the biochemistry panel is presented in [Table 13](#).
- ⁱ Donor-specific antibodies will be measured in both the central and local laboratories. Central laboratory results will be used for analyses. Local laboratory results will be used by the investigator to make treatment decisions, including the initiation of plasmapheresis. Donor-specific antibodies should be tested in the local laboratory within between 24 and 72 hours after completing plasmapheresis.
- ^j Sequential PK **CCI** [REDACTED] sampling from a subset of subjects will occur on the Day 10 and Week 11 Visits. See [Table 6](#) for additional details.
- ^k Intravenous C1-INH will be administered at a dose of 60 IU/kg at the study site. Intravenous C1-INH should be administered with a minimum of 48 hours between each dose.
- ^l Subcutaneous C1-INH will be administered at a dose of 60 IU/kg every 3 or 4 days (ie, twice weekly) at the study site, at home by a medical professional, or at home by the subject under the supervision of a medical professional. The first dose of subcutaneous C1-INH should be administered between 24 and 48 hours after the last dose of intravenous C1-INH.
- ^m Intravenous immunoglobulin will be administered at a dose of 2 grams/kg. Administration of the dose will begin at the visit. The dose must be administered over a minimum period of at least 2 days, and may be administered over a period of up to 5 days (see [Section 5.4.1](#) for details).
- ⁿ **CCI** [REDACTED]
- ^o Responders will be randomized to treatment with blinded investigational product during Treatment Period 2. The definition of response is provided in [Section 10.3.1](#). Non-responders will enter a 45-month Non-responder Follow-up Period.

CSL Behring LLC

CSL842_3001

C1-esterase Inhibitor, Human (500 IU/mL)

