^g If DSA ≥ 2000 MFI, intravenous immunoglobulin may be administered at a dose of 2 grams/kg. Administration of the dose will begin at the visit. The dose must be administered over a minimum period of at least 2 days, and may be administered over a period of up to 5 days.

^h If investigational product will be administered off-site after the completion of the visit, then it will be dispensed to the subject.

CSL Behring LLC

CSL842_3001

C1-esterase Inhibitor, Human (500 IU/mL)

- i Throughout a Retreatment Period, subjects should return any used or partially used vials of investigational product. Subjects should then return all vials (ie, used, partially used, and unused) of investigational product at the Week 26 Retreatment Visit.

Table 6

**Schedule of Assessments: Sequential Pharmacokinetic /
CCI Sampling Conducted in a Subset of Subjects**

Activity	Timepoint	Timepoint Window
Day 10 Visit (Day 10 ± 1 Day)		
Blood Draw	- 30 minutes	± 30 minutes
Intravenous Administration of C1-INH 60 IU/kg	0 minutes	NA
Blood Draw	15 minutes	± 5 minutes
Blood Draw	3 hours	± 30 minutes
Blood Draw	8 hours	± 1 hour
Blood Draw	24 hours	± 6 hours
Blood Draw	48 hours	± 6 hours
Blood Draw	72 hours	± 6 hours
Week 11 Visit (Day 77 ± 2 Days)		
Blood Draw	- 30 minutes	± 30 minutes
Subcutaneous Administration of C1-INH 60 IU/kg	0 minutes	NA
Blood Draw	24 hours	± 6 hours
Blood Draw	48 hours	± 6 hours
Blood Draw	72 hours	± 6 hours

C1-INH = C1-esterase Inhibitor, Human (500 IU/mL).

Note 1: All blood draws will be timed relative to the start of C1-INH administration.

Note 2: CCI

Table of Contents

List of Personnel and Organizations Responsible for Conduct of the Study.....	2
Revision History	3
Protocol Synopsis	7
Table of Contents	23
List of Tables.....	27
List of Figures.....	28
List of Appendices	28
List of Abbreviations	29
Conventions	31
1 Introduction	32
1.1 Background	32
1.2 Background Information on C1-esterase inhibitor	33
1.2.1 Overview	33
1.2.2 Nonclinical Evaluation	34
1.2.3 Clinical Experience with C1-INH in Transplant	34
1.3 Study Overview.....	36
1.4 Potential Risks and Benefits.....	37
2 Study Objectives and Endpoints.....	39
2.1 Primary Objective and Endpoint	39
2.1.1 Primary Objective.....	39
2.1.2 Primary Endpoint	39
2.2 Secondary Objectives and Endpoints	39
2.2.1 Secondary Objectives	39
2.2.2 Secondary Endpoints	40
2.3 CCl.....	
2.3.1	
2.3.2	
3 Study Overview	43
3.1 Study Design	43
3.2 Dose and Dosing Regimen	45

3.3	Scientific Rationale	47

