8.5.3.11 Week 9 and Week 10 Visits

The following procedures will be conducted at the Week 9 and 10 Visits:

- Blood draws:
 - Creatinine.
 - Serum biochemistry panel.
 - C1-esterase inhibitor activity/antigen (Week 10 only).

NOTE: All blood draws should be completed before administration of C1-INH.

- Subcutaneous administration of C1-INH (60 IU/kg, dose rounded to the lowest 1 mL).
- Investigational product dispense, if applicable.
- Investigational product vial return, if applicable.
- Adverse events.
- Concomitant therapies.
- Schedule next visit.

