10.3.5 Pharmacokinetics Analyses

Blood samples will be collected for the assessment of C1-esterase inhibitor antigen concentrations and C1-esterase inhibitor functional activity at designated timepoints. C1-esterase inhibitor functional activity will be determined by a validated assay.

The observed C1-esterase inhibitor antigen concentrations and functional activity will be summarized by time, route of administration, and treatment subgroup (placebo vs C1-INH).

The parameters AUC_{0-t} and C_{max} will be estimated, if feasible, using non-compartmental PK analyses in the subset of ~20 subjects who have more frequent, sequential PK sampling at the Day 10 Visit and the Week 11 Visit.

In addition, population PK analyses may also be conducted and reported separately.

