12.2 Plasma PK Endpoints

The PK parameters based on data collected on Day 10 following IV administration and Week 10 following SC administration will be derived, using Phoenix WinNonlin, Version 8.1 or higher. The PK parameter derivation is based on actual sampling times and includes imputation of the values below the lower limit of quantification (BLQ) and missing data will be conducted in accordance to [CSL SOP PK-GDL-01](#), Guideline on the Conduct of Non-compartmental Pharmacokinetic Analyses, CSL Behring which gives guidance on how to derive PK parameters in the presence of missing data.

Definition of derived PK Parameter:

Term	Definition
AUC _{0-t}	Area under the concentration time curve from time point zero to the last quantifiable time point.
C _{max}	The maximum (peak) observed C1-INH level.
T _{max}	The time to reach C _{max} .

Term	Definition
C_{trough}	Trough C1-INH, collected prior to the next infusion.

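### SAP 12.2 derives the SC PK parameters from Week 10, but the serial SC samples are drawn at Week 11; SAP 12.1 also omits the Day 10 48-hour draw

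*SAP*

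**What the plan says.** **Protocol.** Table 6 sets out two serial profiles for the PK subset. The IV profile is headed "Day 10 Visit (Day 10 ± 1 Day" and has draws 30 minutes before the dose and at 15 minutes, 3, 8, 24, 48 and 72 h. The SC profile is headed "Week 11 Visit (Day 77 ± 2 Days" and has draws 30 minutes before the dose and at 24, 48 and 72 h. The 48 h line, "Blood Draw 48 hours ± 6 hours", appears in both. In each profile, 0 minutes is the administration of C1-INH and not a draw. Table 1 footnote j says that "sampling from a subset of subjects will occur on the Day 10 and Week 11 Visits", and section 10.3.5 bases AUC0-t and Cmax on "sequential PK sampling at the Day 10 Visit and the Week 11 Visit", in about 20 subjects. At the Week 9 and 10 visits (section 8.5.3.11) the only PK item is "C1-esterase inhibitor activity/antigen (Week 10 only", drawn before dosing.

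**SAP.** Section 12.1 gives the Day 10 post-dose times as "15 minutes, 3, 8, 24, and 72 hours after start of infusion" and puts the SC profile at Week 11, with 24, 48 and 72 h. It lists 0 minutes among the sample times of both profiles. Section 12.2 takes the IV parameters from Day 10, but its wording for the SC parameters is "Week 10 following SC administration will be derived". Cmax and AUC0-t after IV and/or SC dosing remain a secondary endpoint (SAP Table 2) and are still to be listed (10.10) and summarized (12.4).

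**The concern.** SAP 12.2 is the operative instruction for computing the PK parameters, and it names a visit that has no profile. It disagrees with the section just before it as well as with the protocol. Taken at its word, it leaves the SC half of a retained secondary endpoint without data for AUC0-t, Cmax and Tmax.

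The 48 h gap in SAP 12.1 is a separate and smaller matter. Concentrations are summarized and plotted (means and medians) at planned times (SAP 7, 12.1 and 12.3). A programmer who builds the planned-time rows from the SAP 12.1 list would have no 48 h row for Day 10, and would have a 0-minute row with no sample to fill it. SAP 12.5 describes datasets passing between groups for parameter derivation, and output being pre-programmed on dummy data before lock. Such slips are therefore better settled in the text than left to be noticed later.

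SAP section 5 lists the analyses changed after termination. Its legible items mention no change to PK sampling, so neither difference is presented as deliberate.

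**Working it through.** There is no figure in the plan to reproduce. The check has three steps.

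**1. The schedules side by side.**

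| Profile | Protocol Table 6 draws | SAP 12.1 sample times | SAP 12.2 source visit |
|---|---|---|---|
| IV | Day 10: pre-dose, 15 min, 3, 8, 24, 48, 72 h (7) | Day 10: pre-dose, 0 min, 15 min, 3, 8, 24, 72 h | Day 10 |
| SC | Week 11: pre-dose, 24, 48, 72 h (4) | Week 11: pre-dose, 0 min, 24, 48, 72 h | Week 10 |

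For IV, SAP 12.1 contains 6 of the 7 protocol draws; the one missing is 48 h. For SC, SAP 12.1 contains all 4. The 0-minute entry is extra in both.

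**2. What Week 10 can yield.** There is one pre-dose sample (protocol 8.5.3.11). A trapezoidal AUC over n samples has n − 1 intervals, so n = 1 gives none. Cmax and Tmax need post-dose observations, and there are none. Ctrough, defined in SAP 12.2 as a level taken before the next dose, could be filled by that sample.

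**3. What losing the 48 h value would do to AUC(0-72 h), if it were lost.** This is illustrative. The documents give neither a half-life nor a trapezoid rule; the derivation rules are in a sponsor guideline that is not part of these documents.

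Assumptions:
- Pre-dose level 1.0 times normal.
- Peak at 15 minutes of 2.3 times normal (the simulated IV peak in protocol 3.3.2, read as a multiple of normal).
- Mono-exponential decline with half-life h from 12 to 72 h, towards a floor F of either 1.0 (endogenous C1-INH) or 0.

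C(t) = F + (2.3 − F) × 2^(−(t − 0.25)/h)

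Only the 24-72 h stretch changes. Under the linear rule, the AUC without 48 h minus the AUC with it is

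48(C24 + C72)/2 − [24(C24 + C48)/2 + 24(C48 + C72)/2] = 12(C24 − 2·C48 + C72).

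- *h = 24, F = 1.0:* C24 = 1.6547, C48 = 1.3274, C72 = 1.1637. The difference is 12 × 0.1637 = 1.96. The AUC with 48 h is 112.43, so the change is 1.96/112.43 = +1.75%.
- *h = 12, F = 0 (largest case):* C24 = 0.5834, C48 = 0.1458, C72 = 0.0365. The difference is 12 × 0.3281 = 3.94. The AUC with 48 h is 0.41 + 5.86 + 8.58 + 16.43 + 8.75 + 2.19 = 42.22, so the change is 3.94/42.22 = +9.33%.

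All cases, as % change in AUC(0-72 h):

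| Half-life (h) | F = 1.0, linear | F = 1.0, linear-up/log-down | F = 0, linear | F = 0, log-down |
|---|---|---|---|---|
| 12 | 2.32 | 2.10 | 9.33 | 0.00 |
| 24 | 1.75 | 1.30 | 4.85 | 0.00 |
| 36 | 1.10 | 0.72 | 2.63 | 0.00 |
| 48 | 0.73 | 0.44 | 1.62 | 0.00 |
| 72 | 0.38 | 0.21 | 0.78 | 0.00 |

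The last column is zero because the log rule integrates a pure exponential exactly. With F = 1.0, pre-dose levels of 1.3 or 1.5 instead of 1.0 leave the percentages unchanged to two decimals. The window stays at 72 h, because the 72 h draw is kept. IV Cmax is unlikely to move.

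**The case against.** The best reply is that these are drafting slips with little practical reach, and most of that stands.

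- SAP 12.1 names Week 11, so an attentive analyst would see that Week 10 in 12.2 is wrong.
- Parameter derivation uses actual sampling times (SAP 7 and 12.2). The concentration data go to the PK analyst as a dataset (SAP 12.5), and nothing tells the analyst to discard samples that SAP 12.1 does not list. A reader might infer that the IV AUC0-t loses its 48 h point. The documents do not support that.
- Nominal times come from the merged concentration and CRF data (SAP 12), and SAP 12.3 does not restrict summaries to the SAP 12.1 list. A 48 h sample could carry its own planned time, so the risk to the summaries and mean plots is real but not certain.
- A reader might infer that no SC parameter at all could be produced. That goes too far, since Week 10 could supply a Ctrough.
- A reader might infer that the endpoint itself is misdefined, or that the 48 h samples were not collected. Neither follows. The endpoint in SAP Table 2 refers to the subset with sequential sampling, which agrees with Table 6, and Table 6 still schedules the draw.
- The study stopped with 13 subjects randomized, no hypothesis is formally tested, and the PK output is descriptive. No inference depends on this point.

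What the reply does not remove is that SAP 12.2, as written, directs a retained analysis to a visit that cannot supply it.

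**Conclusion.** The point holds as a minor inconsistency in the SAP's PK section.

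The Week 10 reference is the more important part. It is wrong against the protocol and against SAP 12.1, and read literally it makes the SC AUC0-t, Cmax and Tmax underivable. That conclusion rests only on the sampling schedules and needs no modelling assumption.

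The missing 48 h time and the misplaced 0-minute entry in SAP 12.1 are smaller. Their likely effect is on planned-time summaries and mean plots, not on the derived parameters. Only if the 48 h values were actually excluded would AUC(0-72 h) change. The change would then be between 0 and about 9% upward, and no more than about 2.3% if levels decline towards a normal endogenous floor. Those percentages depend on the assumed half-life, trapezoid rule and floor, and are a bound on the concern, not an estimate of bias in this trial.

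**What to change.** - **SAP 12.2:** replace Week 10 with Week 11 as the source of the SC parameters.
- **SAP 12.1:** give the Day 10 draws as pre-dose, 15 minutes, 3, 8, 24, 48 and 72 h. In both the Day 10 and Week 11 profiles, show 0 minutes as the dosing time and not as a sample.
- **If any of these differences was intended**, state it in SAP section 5 as a change from the protocol, with the reason.

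The cost is a few words in two adjacent sections. No new data are needed, and the analysis method does not change. The one follow-up is to check that any pre-programmed PK output uses the Week 11 visit and has a 48 h row for Day 10.
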